5.3.7 Safety laboratory parameters

For the assessment of laboratory parameters, blood and urine samples will be collected by the trial site at the time points indicated in [Flow Chart I](#) & [Flow Chart II](#).

If safety laboratory measurement is performed with other blood collection, e.g. PK sampling, safety laboratory measurement will always be performed first, preferably without any tourniquet.

The parameters that will be determined are listed in [Tables 5.3.7: 1](#) and [5.3.7: 2](#). Reference ranges will be provided in the ISF

Manual differential white blood cell count or urine sediment examinations will only be performed if there is an abnormality in the automatic blood cell count or in the urinalysis, respectively.

Table 5.3.7: 1

Routine laboratory tests

| Category | Test name | A¹ | B² | C³ |
|---|--|----------------------|----------------------|----------------------|
| Haematology | Haematocrit | X | X | X |
| | Haemoglobin | X | X | X |
| | Red blood cells (RBC) | X | X | X |
| | White blood cells (WBC) | X | X | X |
| | Platelets | X | X | X |
| | Reticulocyte count | X | X | X |
| Automatic WBC differential (relative and absolute) | Neutrophiles | X | X | X |
| | Eosinophils | X | X | X |
| | Basophils | X | X | X |
| | Monocytes | X | X | X |
| | Lymphocytes | X | X | X |
| Manual differential WBC (if automatic differential WBC is abnormal) | Polymorphnuclear neutrophils (segs), band (only for HV) neutrophils (stabs), eosinophils, basophils, monocytes, lymphocytes | | | |
| Coagulation | Activated partial thromboplastin time (aPTT) | X | X | X |
| | Prothrombin Time (Quick and INR) | X | X | X |
| Enzymes | Aspartate aminotransferase (AST/GOT, SGOT) | X | X | X |
| | Alanine aminotransferase (ALT/GPT, SGPT) | X | X | X |
| | Alkaline phosphatase | X | X | X |
| | Gammaglutamyl transferase (GGT) | X | X | X |
| | Lactate dehydrogenase | X | X | X |
| | Amylase | X | X | X |
| | Lipase | X | X | X |

Table 5.3.7: 1

Routine laboratory tests (cont.)

| Category | Test name | A¹ | B² | C³ |
|---|---|----------------------|----------------------|----------------------|
| Substrates | Glucose (plasma) | X | - | - |
| | Creatinine | X | X | X |
| | eGFR, calculated from serum creatinine using CKD-EPI formula | X | X | X |
| | Bilirubin, total | - | - | - |
| | Bilirubin, direct | X | X | X |
| | Cholesterol, total | X | X | X |
| | Triglycerides | X | X | X |
| | C-reactive protein | X | X | X |
| | Urea | X | X | X |

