Examples of such events are intensive treatment in an emergency room or at home for allergic bronchospasm, blood dyscrasias or convulsions that do not result in hospitalisation or development of dependency or abuse. Any suspected transmission via a medicinal product of an infectious agent is also considered a serious adverse reaction.

AEs considered “Always Serious”

In accordance with the European Medicines Agency initiative on Important Medical Events, Boehringer Ingelheim has set up a list of further AEs, which by their nature, can always be considered to be “serious” even though they may not have met the criteria of an SAE as given above. Cancers of new histology and exacerbations of existing cancer must be reported as a serious event regardless of the duration between discontinuation of the drug and the occurrence of the cancer.

The latest list of “Always Serious AEs” can be found in the Remote Data Capture (RDC) system. These events should always be reported as SAEs as described above.

Adverse events of special interest (AESIs)

The term AESI relates to any specific AE that has been identified at the project level as being of particular concern for prospective safety monitoring and safety assessment within this trial, e.g. the potential for AEs based on knowledge from other compounds in the same class. AESI need to be reported to the sponsor’s Pharmacovigilance Department within the same timeframe that applies to SAE, please see above.

The following are considered as AESIs in this trial:

Hepatic injury

A hepatic injury is defined by the following alterations of hepatic laboratory parameters:

- an elevation of AST and/or ALT ≥ 3 fold ULN combined with an elevation of total bilirubin ≥ 2 fold ULN measured in the same blood draw sample, and/or
- marked peak aminotransferase (ALT, and/or AST) elevations ≥ 10 fold ULN

These lab findings constitute a hepatic injury alert and the subjects showing these lab abnormalities need to be followed up according to the “DILI checklist” provided in the RDC system

In case of clinical symptoms of hepatic injury (icterus, unexplained encephalopathy, unexplained coagulopathy, right upper quadrant abdominal pain, etc.) without lab results

Proprietary confidential information © 2017 Boehringer Ingelheim International GmbH or one or more of its affiliated companies

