(ALT, AST, total bilirubin) available, the Investigator should make sure these parameters are analysed, if necessary in an unscheduled blood test. Should the results meet the criteria of hepatic injury alert, the procedures described in the DILI checklist should be followed.

Intensity of AEs

The intensity of the AE should be judged based on the following:

| | |
|-----------|--|
| Mild: | Awareness of sign(s) or symptom(s) that is/are easily tolerated |
| Moderate: | Enough discomfort to cause interference with usual activity |
| Severe: | Incapacitating or causing inability to work or to perform usual activities |

Causal relationship of AEs

The definition of an adverse reaction implies at least a reasonable possibility of a causal relationship between a suspected medicinal product and an adverse event. An adverse reaction, in contrast to an adverse event, is characterised by the fact that a causal relationship between a medicinal product and an occurrence is suspected.

Medical judgment should be used to determine the relationship, considering all relevant factors, including pattern of reaction, temporal relationship, de-challenge or re-challenge, confounding factors such as concomitant medication, concomitant diseases and relevant history.

Arguments that may suggest that there is a reasonable possibility of a causal relationship could be:

- The event is consistent with the known pharmacology of the drug
- The event is known to be caused by or attributed to the drug class.
- A plausible time to onset of the event relative to the time of drug exposure.
- Evidence that the event is reproducible when the drug is re-introduced
- No medically sound alternative aetiologies that could explain the event (e.g. pre-existing or concomitant diseases, or co-medications).
- The event is typically drug-related and infrequent in the general population not exposed to drugs (e.g. Stevens-Johnson syndrome).
- An indication of dose-response (i.e. greater effect size if the dose is increased, smaller effect size if dose is diminished).

Arguments that may suggest that there is no reasonable possibility of a causal relationship could be:

- No plausible time to onset of the event relative to the time of drug exposure is evident (e.g. pre-treatment cases, diagnosis of cancer or chronic disease within days / weeks of drug administration; an allergic reaction weeks after discontinuation of the drug concerned)

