the Investigator does not need to actively monitor the subject for AEs but should only report relevant SAEs and relevant AESIs of which the Investigator may become aware of.

The REP for BI 433651 is defined as 30 days after the last trial medication application. All AEs which occurred through the treatment phase and throughout the REP will be considered as on treatment, please see [Section 7.3.4](#). Events which occurred after the REP and before trial termination date will be considered as follow-up events.

AE reporting to sponsor and timelines

The Investigator must report SAEs, AESIs, and non-serious AEs which are relevant for the reported SAE or AESI, on the BI SAE form via fax immediately (within 24 hours) to the sponsor's unique entry point (country specific contact details will be provided in the ISF). The same timeline applies if follow-up information becomes available. In specific occasions the Investigator could inform the sponsor upfront via telephone. This does not replace the requirement to complete and fax the BI SAE form.

With receipt of any further information to these events, a follow-up SAE form has to be provided. For follow-up information the same rules and timeline apply as for initial information.

Information required

For each AE, the Investigator should provide the information requested on the appropriate CRF pages and the BI SAE form. The Investigator should determine the causal relationship to the trial medication and any possible interactions between the investigational drug and a Non-Investigational Medicinal Product (NIMP).

The following should also be recorded as an (S)AE in the CRF and SAE form (if applicable):

- Worsening of the underlying disease or of other pre-existing conditions
- Changes in vital signs, ECG, physical examination and laboratory test results, if they are judged clinically relevant by the Investigator.

If such abnormalities already pre-exist prior trial inclusion they will be considered as baseline conditions.

All (S)AEs, including those persisting after individual subject's end of trial must be followed up until they have resolved, have been sufficiently characterised, or no further information can be obtained.

Pregnancy

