6.2.3 End of Trial Period

For AE assessment, laboratory tests, recording of ECG and vital signs, physical examination, weight and pregnancy test for female subjects of child bearing potential, during the end of trial period, [see Sections 5.3.1](#) to [5.3.7](#).

Subjects who discontinue treatment before the end of the planned treatment period should undergo the follow-up and end of trial visit.

All abnormal values (including laboratory parameters) that are judged clinically relevant by the investigator will be monitored using the appropriate tests until a return to a medically acceptable level is achieved. Adverse events persisting after trial completion must be monitored until they have normalised or have been sufficiently characterised.

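### Table 5.3.7: 1 never schedules total bilirubin, so the combined criterion of the hepatic-injury AESI cannot be evaluated from the scheduled samples

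*Protocol*

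**What the plan says.** Protocol Section 5.3.7 makes its tables the governing list: "The parameters that will be determined are listed in" Tables 5.3.7: 1 and 5.3.7: 2. Table 5.3.7: 1 has three columns: A for screening, B for during the study and C for follow-up. The row "Bilirubin, total" has a dash in each. The next row reads "Bilirubin, direct | X | X | X", and ALT and AST are also marked in all three.

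Section 5.3.10.1 lists one AESI, hepatic injury, with two criteria joined by and/or. The first is AST and/or ALT of at least 3 times ULN "combined with an elevation of total bilirubin" of at least 2 times ULN in the same blood draw. The second is "marked peak aminotransferase (ALT, and/or AST) elevations" of at least 10 times ULN.

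If clinical symptoms of hepatic injury appear and ALT, AST and total bilirubin results are not available, "the Investigator should make sure these parameters are analysed, if necessary in an unscheduled blood test".

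SAP Section 7.8.1 takes the AESI definition from the protocol unchanged and plans a separate table of subjects with AESIs.

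**The concern.** The laboratory schedule and the AESI definition contradict each other: the definition relies on an analyte that the schedule says is not determined. Section 2.3.2 requires liver laboratory changes to be found and followed up in good time, and AESIs carry the 24-hour reporting timeline of SAEs. Neither can be met for a value that is not measured. Clinical laboratory tests are also part of the minimum data set for the dose-escalation reviews (Section 3.1.2). In the SAP's AESI table, a zero could mean that the combined criterion was not assessed rather than that no case occurred.

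**Working it through.** No arithmetic beyond counting applies. The check compares what each AESI criterion needs with what Table 5.3.7: 1 provides.

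| Analyte | A | B | C | Needed for 3x/2x criterion | Needed for 10x criterion |
|---|---|---|---|---|---|
| ALT, AST | X | X | X | yes | yes |
| Total bilirubin | - | - | - | yes | no |
| Direct bilirubin | X | X | X | no | no |

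1. **Columns marked.** Total bilirubin 0 of 3; ALT, AST and direct bilirubin 3 of 3 each. One of the two AESI criteria therefore lacks an input.

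2. **Subjects affected.** The row has no population limit, so it covers 40 healthy volunteers + 24 CF subjects = 64 planned subjects.

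3. **Sampling occasions.** In Flow Chart I, the full-panel footnote 3 is attached to 4 individual cells: screening, Day -7 to -3, Day 7 pre-dose and end of study. Two of these (Day 7 and end of study) fall after first dose. As tabulated, total bilirubin is determined at none of them.

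4. **Can direct bilirubin stand in?** Only in one direction. Direct is a component of total, so direct is at most equal to total. A direct value at or above 2 times the ULN for total would prove the threshold was met. A normal or modestly raised direct value leaves the total unknown. The urine-stick bilirubin does not give a serum total.

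5. **Is total bilirubin scheduled elsewhere?** No. The flow-chart footnotes refer back to Section 5.3.7. Table 5.3.7: 2 holds only the urine drug screen and infectious serology. The visible amendment log shows no correction of the row. The SAP lists no analytes of its own.

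6. **Unscheduled routes.**
   - The symptom-triggered test names total bilirubin but does not apply to a subject without symptoms.
   - Section 5.3.10.2 has the investigator record "Changes in vital signs, ECG, physical examination and laboratory test results, if they are judged clinically relevant by the Investigator", and Section 6.2.3 says abnormal values "that are judged clinically relevant by the investigator will be monitored using the appropriate tests". Both depend on the investigator's judgement, and neither names total bilirubin.
   - The DILI checklist follows once the laboratory criteria are met, so it cannot be the first source of a value that triggers it.

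What remains uncovered is a symptom-free subject with ALT or AST from 3 to below 10 times ULN and raised total bilirubin.

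**The case against.** The strongest reply is that this is a clerical slip of limited consequence. It is the only row in the table with a dash in all three columns, and there is no reason to list a test that is never done; the total and direct rows may have been interchanged. Section 5.3.7 also says the central laboratory performs the listed tests, and total bilirubin is listed. The real panel is in the Central Laboratory Manual, which is not among the documents. ALT, AST, alkaline phosphatase and GGT are all scheduled, so the enzyme rise that would start a work-up is still seen. Section 2.3.2 identifies electrolyte changes, not liver injury, as the expected systemic risk, and no withdrawal or stopping rule uses bilirubin.

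Much of this stands. The gap is narrow, and a slip is the likelier explanation. But a slip in the operative schedule still needs correcting, because a laboratory or site that follows it as printed will not measure the analyte.

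Three further points also stand:
- SAP Section 7.8.1 lists AESI among the AE attributes on the eCRF and describes no derivation from laboratory values. A zero in the AESI table therefore depends on investigator reporting in any case; non-measurement is one possible contributor.
- The count of 4 cells is approximate. Footnote 3 is also on the column header, and the Day 7 cell additionally carries the electrolytes-only footnote 8. No equivalent count was made for Flow Chart II.
- Part 1 was to be locked and analysed separately, so for those samples disclosure may be the only practical remedy.

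**Conclusion.** The concern holds, and the row must be corrected. As printed, scheduled samples cannot settle one of the two criteria of the trial's only listed AESI in any subject, except where a very high direct bilirubin settles it by itself. The 10 times ULN criterion remains usable. The primary endpoint, sample size and numeric stopping thresholds are not affected.

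The contradiction in the text is certain, assuming the row's three dashes were read correctly from the PDF; the rows around it are intact. Its effect on the data is not known. If the central laboratory did assay total bilirubin, only the table is wrong. If it did not, the combined criterion was unassessed in symptom-free subjects unless an investigator ordered the test.

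**What to change.** Reconcile Table 5.3.7: 1 with Section 5.3.10.1 by marking total bilirubin as determined in columns A, B and C, and confirm that it is on the central laboratory panel. This costs one table row and, from then on, one routine assay on blood already drawn for ALT and AST, with no extra visit or draw.

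If samples already taken were not assayed for it, add one sentence to the SAP and the CTR stating that the combined hepatic-injury criterion was not assessable at those visits, with a matching footnote to the AESI table so that a zero is not read as absence of cases.

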5.3.10 Assessment of adverse events

5.3.10.1 Definitions of Adverse Events (AEs)

Adverse event

An adverse event (AE) is defined as any untoward medical occurrence in a subject or clinical investigation subject administered a medicinal product and which does not necessarily have to have a causal relationship with this treatment.

An AE can therefore be any unfavourable and unintended sign (including an abnormal laboratory finding), symptom, or disease temporally associated with the use of a medicinal product, whether or not considered related to the medicinal product.

Adverse reaction

An adverse reaction is defined as a response to a medicinal product which is noxious and unintended. Response in this context means that a causal relationship between a medicinal product and an adverse event is at least a reasonable possibility. Adverse reactions may arise from use of the product within or outside the terms of the marketing authorisation or from occupational exposure. Conditions of use outside the marketing authorization include off-label use, overdose, misuse, abuse and medication errors.

Serious adverse event

A serious adverse event (SAE) is defined as any AE which:

- results in death,
- is life-threatening, this refers to an event in which the subject was at risk of death at the time of the event; it does not refer to an event that hypothetically might have caused death if more severe.
- requires inpatient hospitalisation or
- prolongation of existing hospitalisation,

Proprietary confidential information © 2017 Boehringer Ingelheim International GmbH or one or more of its affiliated companies

- results in persistent or significant disability or incapacity, or
- is a congenital anomaly / birth defect, or
- is to be deemed serious for any other reason if it is an important medical event when based upon appropriate medical judgment which may jeopardise the subject and may require medical or surgical intervention to prevent one of the other outcomes listed in the above definitions.

Medical and scientific judgement should be exercised in deciding whether other situations should be considered serious reactions, such as important medical events that might not be immediately life threatening or result in death or hospitalisation but might jeopardise the subject or might require intervention to prevent one of the other outcomes listed above.

Examples of such events are intensive treatment in an emergency room or at home for allergic bronchospasm, blood dyscrasias or convulsions that do not result in hospitalisation or development of dependency or abuse. Any suspected transmission via a medicinal product of an infectious agent is also considered a serious adverse reaction.

AEs considered “Always Serious”

In accordance with the European Medicines Agency initiative on Important Medical Events, Boehringer Ingelheim has set up a list of further AEs, which by their nature, can always be considered to be “serious” even though they may not have met the criteria of an SAE as given above. Cancers of new histology and exacerbations of existing cancer must be reported as a serious event regardless of the duration between discontinuation of the drug and the occurrence of the cancer.

The latest list of “Always Serious AEs” can be found in the Remote Data Capture (RDC) system. These events should always be reported as SAEs as described above.

Adverse events of special interest (AESIs)

The term AESI relates to any specific AE that has been identified at the project level as being of particular concern for prospective safety monitoring and safety assessment within this trial, e.g. the potential for AEs based on knowledge from other compounds in the same class. AESI need to be reported to the sponsor’s Pharmacovigilance Department within the same timeframe that applies to SAE, please see above.

The following are considered as AESIs in this trial:

Hepatic injury

A hepatic injury is defined by the following alterations of hepatic laboratory parameters:

- an elevation of AST and/or ALT ≥ 3 fold ULN combined with an elevation of total bilirubin ≥ 2 fold ULN measured in the same blood draw sample, and/or
- marked peak aminotransferase (ALT, and/or AST) elevations ≥ 10 fold ULN

These lab findings constitute a hepatic injury alert and the subjects showing these lab abnormalities need to be followed up according to the “DILI checklist” provided in the RDC system

In case of clinical symptoms of hepatic injury (icterus, unexplained encephalopathy, unexplained coagulopathy, right upper quadrant abdominal pain, etc.) without lab results

Proprietary confidential information © 2017 Boehringer Ingelheim International GmbH or one or more of its affiliated companies

(ALT, AST, total bilirubin) available, the Investigator should make sure these parameters are analysed, if necessary in an unscheduled blood test. Should the results meet the criteria of hepatic injury alert, the procedures described in the DILI checklist should be followed.

Intensity of AEs

The intensity of the AE should be judged based on the following:

| | |
|-----------|--|
| Mild: | Awareness of sign(s) or symptom(s) that is/are easily tolerated |
| Moderate: | Enough discomfort to cause interference with usual activity |
| Severe: | Incapacitating or causing inability to work or to perform usual activities |

Causal relationship of AEs

The definition of an adverse reaction implies at least a reasonable possibility of a causal relationship between a suspected medicinal product and an adverse event. An adverse reaction, in contrast to an adverse event, is characterised by the fact that a causal relationship between a medicinal product and an occurrence is suspected.

Medical judgment should be used to determine the relationship, considering all relevant factors, including pattern of reaction, temporal relationship, de-challenge or re-challenge, confounding factors such as concomitant medication, concomitant diseases and relevant history.

Arguments that may suggest that there is a reasonable possibility of a causal relationship could be:

- The event is consistent with the known pharmacology of the drug
- The event is known to be caused by or attributed to the drug class.
- A plausible time to onset of the event relative to the time of drug exposure.
- Evidence that the event is reproducible when the drug is re-introduced
- No medically sound alternative aetiologies that could explain the event (e.g. pre-existing or concomitant diseases, or co-medications).
- The event is typically drug-related and infrequent in the general population not exposed to drugs (e.g. Stevens-Johnson syndrome).
- An indication of dose-response (i.e. greater effect size if the dose is increased, smaller effect size if dose is diminished).

Arguments that may suggest that there is no reasonable possibility of a causal relationship could be:

- No plausible time to onset of the event relative to the time of drug exposure is evident (e.g. pre-treatment cases, diagnosis of cancer or chronic disease within days / weeks of drug administration; an allergic reaction weeks after discontinuation of the drug concerned)
- Continuation of the event despite the withdrawal of the medication, taking into account the pharmacological properties of the compound (e.g. after 5 half-lives). Of note, this criterion may not be applicable to events whose time course is prolonged despite removing the original trigger.

- Additional arguments amongst those stated before, like alternative explanation (e.g. situations where other drugs or underlying diseases appear to provide a more likely explanation for the observed event than the drug concerned).
- Disappearance of the event even though the study drug treatment continues or remains unchanged.

